### 5.2 Secondary Outcomes

1. Time to recovery, which is the time to the earlier of final liberation from supplemental oxygen or hospital discharge
2. Hospital mortality to 28-day mortality (assessed on Study Day 29 from randomization)
3. Time to discharge to 28 days after treatment
4. Quantitative change in nasal viral titer
5. Change in systemic CD4+ and CD8+ T cell cytokine expression
6. Change in Oxygen AUC of SaO2/FiO2 through Day 7
7. Quantitative change in systemic immune profile
8. Oxygen-free days through Day 28
9. Ventilator-free days through Day 28
10. Vasopressor-free days through Day 28
11. ICU-free days through Day 28
12. Hospital-free days through Day 28

### 5.3 Safety outcomes

- Dehydration
- Symptomatic Hypotension
- Acute kidney injury
- Receipt of renal replacement therapy

### 5.4 Rationale for Primary Outcome

COVID-19 has a broad spectrum of clinical severity. Even among hospitalized patients, most recover without experiencing critical illness. Designing a trial with statistical power to detect a meaningful difference in ICU-free days or mortality might require an unfeasibly large sample size and could miss significant morbidity experienced by the majority of hospitalized patients. Since the majority of morbidity from COVID-19 relates to hypoxemia, the fact that this outcome is tied to degree of hypoxic respiratory failure increases its face validity and relevance. For similar reasons, previous trials of severe influenza have employed a similar ordinal outcome.

This ordinal scale has been selected as an outcome in multiple ongoing COVID-19 trials and is a preferred outcome by the World Health Organization Research and Development Blueprint for COVID-19. Use of this standardized outcome will increase the potential to compare the results of this trial with other trials and perform meta-analyses.

## **6. STUDY ASSESSMENTS, PROCEDURES AND DATA COLLECTION**

Given the infectious risk from COVID-19 and potential shortages of personal protective equipment (PPE), we will minimize face-to-face contact between patients and non-clinical staff. Additionally, minimizing research activities and conducting the trial in a pragmatic manner will increase the ability to complete the trial in the face of strained clinical and research resources during the COVID-19 pandemic. We will emphasize data that can be collected from the electronic health record, radiographs obtained as part of routine clinical care, and assessments that can be completed over the telephone as needed.

### **6.1 Baseline Assessments and Procedures: Hospital Presentation to Randomization (Day 1)**

- Inclusion/exclusion criteria screening
- Pregnancy test (if applicable)
- Informed consent
- Completion of COVID Ordinal Outcomes Scale
- Blood collection for CD4+ and CD8+ T cell cytokine expression
- Nasal Swab testing for SARS-CoV-2
- Completion of the Sequential Organ Failure Assessment (SOFA)
- Evaluation of Acute Respiratory Distress Syndrome (ARDS) by Berlin Criteria
- Baseline Variable Data Collection:
  - Hospital admissions data: date/time of presentation, origin (home, skilled nursing facility, rehabilitation/LTACH, nursing home, outside hospital, outside ICU), location at enrollment (ED, hospital ward, ICU)
  - Demographics (age, sex, race, ethnicity, height, weight)
  - Signs and symptoms/onset date including acute signs/symptoms such as altered mental status, acute hypoxemic respiratory failure, liver function tests, renal function, coagulation studies, SOC chest imaging results
  - Concomitant Medications/Medication History to include:
    - Chronic use of medications such as: corticosteroids, ACE inhibitors, angiotensin receptor blockers, non-steroids or anti-inflammatory drugs
    - Open label antivirals received such as remdesivir
    - Open label immunomodulators
    - Biologic therapy such a convalescent plasma
  - Comorbidities
  - Oxygen/ventilation assessment including S/F ratio, ventilation type, & vasopressor use (if applicable)
  - Vital signs, including highest respiratory rate, lowest systolic blood pressure, and highest heart rate in the 12 hours prior to enrollment (if available)
- Enrollment/Randomization
- First study drug administration

## **6.2 Study Assessments/Procedures: Randomization to Hospital Discharge (Daily)**

- Study Variable Data Collection
  - Medication Assessment
  - Assess for clinical diagnosis of deep vein thrombosis (DVT) or pulmonary embolism (PE)
  - Oxygen/Ventilation assessment including S/F ratio, ventilation type, & vasopressor use (if applicable)
  - ARDS Assessment by Berlin Diagnostic Criteria (if applicable)
  - ICU admission/discharge information (if applicable)
  - Death date (if applicable)
  - Safety Outcomes: Dehydration, Seizure, Atrial or ventricular arrhythmia, Cardiac arrest, Symptomatic Hypotension, Acute kidney injury, Receipt of renal replacement therapy, Symptomatic hypoglycemia
  - Hospital discharge including patient destination at discharge

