## **9. RISK ASSESSMENT**

### **9.1 Potential Risk to Participants**

Although both magnesium citrate and the probiotic Floranex are FDA approved medications with an established safety profile, potential risks exist to participating in this study of magnesium citrate plus the probiotic Floranex versus placebo for the treatment of COVID-19. Mild hypermagnesemia (increases of >1meq) are typical because the majority of the medication remains intraluminal. Patients with renal insufficiency (<30cc/min) are at risk for greater increases in systemic magnesium levels and thus they will be excluded from study participation. Below, we outline side effects based on serum magnesium levels.

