#### **9.1.1 Potential risks of receiving magnesium citrate**

Common Side effects of magnesium citrate include:

Abdominal cramping

Diarrhea

Electrolyte imbalance

Gas (flatulence)

Nausea

Vomiting

Hypermagnesemia (high levels of magnesium in the blood).

Side effects that can occur with Hypermagnesemia:

Nervous system

- Muscle weakness, decrease in tendon reflexes, mental confusion, or sedation when serum magnesium (Mg) levels increase to 4 to 7 mEq/L,
- Slowed respiratory rate and hypotension when serum magnesium (Mg) levels increase to 5 to 10 mEq/L

- Profound mental depression, areflexia, coma and respiratory paralysis when serum Mg levels increase to 10 to 15 mEq/L
- Death possible when serum Mg levels rise to 15 mEq/L or higher.

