# **11. ADVERSE EVENTS**

Assuring patient safety is an essential component of this protocol. Magnesium citrate has been approved by the Food and Drug Administration and used in clinical practice for decades with an established safety profile. Use of magnesium citrate plus the probiotic Floranex for the treatment of acute respiratory infection due to COVID-19, however, raises unique safety considerations. This protocol addresses these considerations through:

1. Exclusion criteria designed to prevent enrollment of patients likely to experience adverse events with receipt of magnesium citrate or the probiotic Floranex, such as those with creatinine clearance of <30cc/min;
2. Proactive education of treating clinicians regarding medication interactions relevant to use of magnesium citrate plus the probiotic Floranex in the inpatient setting;
3. On-study monitoring of co-interventions (e.g., medications) and patient characteristics (e.g., EKG) to intervene before adverse events occur;
4. Systematic collection of safety outcomes relevant to use of magnesium citrate plus the probiotic Floranex in this setting;
5. Structured reporting of adverse events

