## 11.2 Safety Monitoring

Assuring patient safety is an essential component of this protocol. Each participating investigator has primary responsibility for the safety of the individual participants under his or her care. The Investigators will determine daily if any adverse events occur during the period from enrollment through **study day 7** or hospital discharge, whichever occurs first and will determine if such adverse events are reportable. Thereafter, adverse events are not required to be reported unless the investigator feels the adverse event was related to study drug or study procedures.

The following adverse events will be considered reportable and thus collected in the adverse event case report forms:

- Serious adverse events
- Non-serious adverse events that are considered by the investigator to be related to study procedures or of uncertain relationship (Appendix C)
- Events leading to permanent discontinuation of study drug

Study-specific clinical outcomes (Primary, Secondary and Safety Outcomes and Assessments During the Study), including serious outcomes such as organ failures and death, are systematically recorded in the case report forms and are exempt from adverse event reporting unless the investigator deems the event to be related to the administration of study drug or the conduct of study procedures (or of uncertain relationship) as outlined in Appendix C.

After randomization, adverse events must be evaluated by the investigator. If the adverse event is judged to be reportable, as outlined above, then the investigator will report to the Clinical Coordinating Center (CCC) their assessment of the potential relatedness of each adverse event to the study drug or protocol procedure via electronic data entry. Investigators will assess if there is a reasonable possibility that the study procedure caused the event, based on the criteria outlined in Appendix C. Investigators will also consider if the event is unexpected. Unexpected adverse events are events not listed in the study protocol and the package insert for the study drugs will also determine if adverse events are unanticipated given the patient's clinical course, previous medical conditions, and concomitant medications.

If a patient's treatment is discontinued as a result of an adverse event, study site personnel must also report the circumstances and data leading to discontinuation of treatment in the adverse event case report forms.

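### The safety outcome lists in 5.3 and 6.2 differ and omit the electrolyte and gastrointestinal risks named in 9.1, so non-serious events of these kinds are recorded mainly through a causality judgement

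*Combined protocol and SAP*

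**What the plan says.** Section 5.3 names four safety outcomes: dehydration, "Symptomatic Hypotension", acute kidney injury and "Receipt of renal replacement therapy". Section 6.2, which governs daily data collection in hospital, names eight: "Safety Outcomes: Dehydration, Seizure, Atrial or ventricular arrhythmia, Cardiac arrest, Symptomatic Hypotension, Acute kidney injury, Receipt of renal replacement therapy, Symptomatic hypoglycemia".

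Section 9.1 describes the risks of the intervention. It states: "Mild hypermagnesemia (increases of >1meq) are typical because the majority of the medication remains intraluminal". Section 9.1.1 lists seven common side effects of magnesium citrate, among them "Electrolyte imbalance" and "Hypermagnesemia (high levels of magnesium in the blood", together with cramping, diarrhea, gas, nausea and vomiting. It then adds hypocalcemia and paralytic ileus. Section 9.1.2 adds bloating for the probiotic.

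Section 11 counts among the trial's safeguards "Systematic collection of safety outcomes relevant to use of magnesium citrate plus the probiotic Floranex in this setting".

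Section 11.2 sets out which adverse events reach the case report form: serious events, events that permanently stop the study drug, and "Non-serious adverse events that are considered by the investigator to be related to study procedures or of uncertain relationship". After Day 7 or discharge, whichever comes first, reporting is required only for events the investigator considers related.

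**The concern.** A safety outcome list does one thing that adverse event reporting does not: it asks the same question of every patient in both arms, whatever anyone thinks caused the event. The protocol uses that route for eight outcomes but not for the laboratory and gut effects it names as this treatment's risks. Those go through a rule under which a non-serious event is recorded only after a judgement on cause, unless it stops the drug.

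The protocol gives safety as part of the trial's purpose (Section 2.1). It also treats hypermagnesemia and uncorrected potassium or calcium disturbance as reasons to bar entry (Section 3, Exclusion Criteria). Yet neither Section 6 nor Appendix A asks for these to be recorded after dosing. At stake is whether the final report can state, by arm, how many patients had an abnormal magnesium, potassium or calcium value or vomited, with a denominator.

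The difference between the lists matters in its own right. Whoever writes the safety table could follow either section and produce a different set of outcomes.

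**Working it through.** The plan states no figure on this point, so the check is a comparison of lists, followed by one illustrative calculation.

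**Step 1. Compare the two lists, and set both against Section 9.1.**

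| Outcome | 5.3 | 6.2 | Matching risk in 9.1 |
|---|---|---|---|
| Dehydration | yes | yes | not named; plausible consequence of diarrhea |
| Symptomatic hypotension | yes | yes | hypotension |
| Acute kidney injury | yes | yes | not named |
| Renal replacement therapy | yes | yes | not named |
| Atrial or ventricular arrhythmia | no | yes | bradyarrhythmia |
| Cardiac arrest | no | yes | asystole |
| Seizure | no | yes | not named |
| Symptomatic hypoglycemia | no | yes | not named |

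All 4 items of 5.3 appear in 6.2, and 8 − 4 = 4 items appear only in 6.2. Two of those four, arrhythmia and cardiac arrest, correspond to cardiac effects of high magnesium. A table built from 5.3 would leave them out.

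**Step 2. Look for the named electrolyte and gastrointestinal risks.** Section 9.1.1 gives 7 common side effects: cramping, diarrhea, electrolyte imbalance, gas, nausea, vomiting and hypermagnesemia. Hypocalcemia, paralytic ileus and bloating bring the total to 7 + 3 = 10. The number found on either list is 0 of 10. Appendix C.3 has gastrointestinal items, but they are transaminase elevation and pancreatitis, which are not among the ten.

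**Step 3. Look for another systematic source.** The Day 7 blood draw in Section 6.2.1.3 is for T cell cytokine expression. Neither Section 6 nor Appendix A schedules magnesium or electrolytes after randomization. An abnormality without symptoms is therefore seen only if routine care tests for it.

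**Step 4. Follow a non-serious event through the reporting rule.** Take a low potassium value on Day 2 that does not stop the drug. Under Section 11.2 it is recorded only if graded related or uncertain. Appendix C.2 grades an event as probably not related when the patient's condition or other treatment can reasonably explain it; it grades an event as probably or possibly related when some, but not all, criteria for a definite link are met. In an acutely ill inpatient either grade can be defended. One leads to a record and the other does not.

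**Step 5. Illustrate what 15 per arm can show.** The documents give no event rates, so all rates here are assumptions. Power is the sum, over all pairs (a, b), of Bin(a; 15, p1) × Bin(b; 15, p2), counting the pairs with a two-sided Fisher exact p ≤ 0.05.

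- 10% vs 30%: 15%
- 20% vs 50%: 25%
- 10% vs 50%: 54%
- 10% vs 60%: 74%
- 20% vs 80%: 87%
- 10% vs 80%: 98%

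If only half of events pass the causality judgement in both arms, 10% vs 60% becomes 5% vs 30%, and power falls from 74% to about 28%. Formal comparison works only for very large differences, and incomplete recording erodes even that.

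**The case against.** The strongest reply is that much of the expected harm is already collected. Symptomatic hypotension, dehydration and acute kidney injury are on both lists; arrhythmia and cardiac arrest are in 6.2. Section 11.3 collects serious adverse events until discharge whatever their cause, and Appendix A schedules adverse event assessment on Days 1 to 7 and Day 29. All of this stands. A reader might infer from the gap that the trial cannot compare expected harms between arms. The documents do not support that: the gap concerns non-serious electrolyte and gastrointestinal events.

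Second, the rule is not especially restrictive. Appendix C.2 has an uncertain category, which is reportable, and an event soon after dosing that the protocol names as a side effect is hard to call unrelated. This makes full suppression unlikely, but it does not make recording uniform. Expectedness plays no part in whether a non-serious event is recorded under Section 11.2, so the gap should not be attributed to it.

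Third, a reader might infer that the rule hides harm in the active arm. Section 3.7 keeps personnel and assessors blinded. If the laxative effect reveals the arm, investigators might attribute more events to the drug, not fewer. The direction is unknown, and only the possibility of differential recording can be claimed.

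Fourth, the lists are uneven rather than contradictory, since 5.3 is a subset of 6.2. Seizure and hypoglycemia appear in Appendix C.3 as study-specific outcomes, so their presence is not in itself an error. Both points stand.

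Finally, diarrhea is what a colonic cleanser is meant to produce, so counting it as harm would largely measure drug action. This also stands and shapes the remedy.

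**Conclusion.** The point holds in limited form. The lists have 4 and 8 items and need to be reconciled. None of the 10 electrolyte or gastrointestinal risks named in Section 9.1 is on either, which falls short of the commitment in Section 11. Between-arm comparison of the non-serious forms of these events rests on causality-filtered reports and on whatever routine care happens to measure. It is incomplete and could be distorted in either direction.

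The size of any distortion cannot be derived from the documents, because it depends on unknown event rates and on how investigators grade cause. The power figures rest on assumed rates and serve only to show that 15 per arm supports description rather than testing. The formal aims in Section 2.2 concern efficacy, so this does not threaten the primary analysis. It does weaken the safety account, and the correction is cheap enough that it should be made.

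**What to change.** 1. Use one safety outcome list, worded identically in 5.3 and 6.2.
2. Add post-dose magnesium, potassium and calcium abnormalities, and vomiting. Potassium comes under the electrolyte imbalance named in 9.1.1 and is cited in the exclusion criteria. Define the abnormal ranges and the time window in advance.
3. Abstract these in both arms from routine laboratory results and the health record, which Section 6 already favors. No new blood sampling is needed.
4. Report by arm, descriptively, regardless of attributed cause: n/N tested for laboratory items and n/N for vomiting.
5. Report diarrhea separately as a drug effect or tolerability measure, taken from the record so that a daily question does not cue blinded staff.
6. State how the added items relate to the exemption in Section 11.2, which removes safety outcomes from adverse event reporting unless they are judged related or uncertain.

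The cost is a few case report form fields and some abstraction time. Routine tests will be missing for some patients, and clinicians may test selectively, which could bias a comparison this small; the number tested per arm must therefore accompany every count. Cramping, gas, nausea and bloating would stay with adverse event reporting, and that limit should be stated.

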### **6.2.1 Day Specific Assessments: Randomization to Hospital Discharge**

#### **6.2.1.1 Days 2-7 (Daily)**

- COVID Ordinal Outcomes Scale
- Study Drug Adherence Assessment (days 1-6)
- Assessment of Antibiotic Use including azithromycin

#### **6.2.1.2 Day 3**

- Completion of SOFA assessment
- Nasal swab for SARS CoV-2 testing

#### **6.2.1.3 Day 7**

- Blood collection for CD4+ and CD8+ T cell cytokine expression

## **6.3 Assessments following Hospital Discharge**

### **6.3.1 Acute Care Follow-up**

For participants discharged from the study hospital prior to the Day 7 or Day 29 assessment, we will perform these assessments via telephone follow-up. The Day 7 call window will be Day 7 through day 14. The Day 29 call window will be Day 29 through day 36. During these telephone calls, we will interview the patient, LAR, or facility staff to assess:

- Date of death (if applicable)
- ED visits, hospital readmissions, and use of supplemental oxygen after hospital discharge
- Non-laboratory safety outcomes after hospital discharge and adverse events
- Symptoms of acute respiratory infection
- COVID Ordinal Outcomes Scale

### **6.3.2 Long-term Follow-up**

We will follow-up selected patients at 3months to assess vital status, cognition, basic and instrumental activities of daily living, quality of life, employment status, physical disability, and psychological distress (i.e., depression, post-traumatic stress disorder, etc.), place of residence, and rehospitalizations. These assessments may occur by phone, in-person, or videoconferencing.

## 7. STATISTICAL CONSIDERATIONS

### 7.1 Statistical Approach

The primary analysis will be an intention-to-treat comparison of the Day 7 COVID Ordinal Outcome score between patients randomized to magnesium citrate plus a the probiotic Floranex versus placebo. This analysis will be conducted with a proportional odds model using the Day 7 COVID Ordinal Outcome score as the dependent variable, randomized group assignment as the primary independent variable, and the following co-variables: age, sex, baseline COVID Ordinal Outcome score, baseline SOFA score, and duration of acute respiratory infection symptoms prior to randomization. An odds ratio  $>1.0$  indicates more favorable outcomes with magnesium citrate plus the probiotic Floranex on the COVID Ordinal Outcome scale, while an odds ratio  $<1.0$  indicates more favorable outcomes with placebo.

In addition to reporting data for the full trial population we will also report data separately for patients randomized in the ICU (who tend to be more severely ill) and those randomized outside the ICU (who tend to be less severely ill) as well as those with duration of symptoms  $\leq 5$  days prior to randomization and those with  $>5$  days of symptoms prior to randomization.

The anticipated study size is 30 patients. We calculated the sample size under the assumption that we would have an interim analysis after approximately each 10 patients. We calculated the standard error of the log(odds-ratio) statistic with 15 patients per arm based on data from a recently completed trial within the PETAL Network that enrolled patients early in the course of critical illness, the *Vitamin D to Improve Outcomes by Leveraging Early Treatment* (VIOLET) trial. In the VIOLET trial at Day 15, 11.5% of patients had died, 5.8% were on invasive mechanical ventilation, 22.9% remained in the hospital, and the remaining had been discharged from the hospital (Table 1). We used these outcomes in VIOLET to approximate Day 7 outcomes on the COVID Ordinal Outcome scale that we may observe in this trial.

Table 1. Patient status 14 days (“Day 15”) after randomization in the VIOLET trial.

Patient Status	Percentage of patients
Deceased	11.5%
Invasive mechanical ventilation	5.8%
Hospitalized, not on invasive mechanical ventilation	21.9%
Discharged from the hospital	60.8%

We plan to use a Bayesian analysis of the evolving data which allows flexibility in the number and timing of the interim analyses. If we determine there is  $>95\%$  probability of the odds ratio being  $>1.0$ , the DSMB should consider stopping the trial for efficacy. If we determine there is  $>90\%$  probability that the odds ratio is  $<1.1$ , the DSMB should consider stopping the trial for futility. If we determine there is  $>70\%$  probability that the odds ratio is  $<0.70$ , the DSMB should consider stopping the trial for harm. We will use a prior odds ratio of 1.0 (equal chance of harm and benefit; mean log OR of 0.0) and a prior distribution of the standard error for its log set at 0.352 for tests of efficacy and a non-informative prior for tests of futility and harm. The results will be reported in a similar manner to those published by Goligher et al. One advantage of Bayesian analysis is that stopping guidelines are not binding and the DSMB is charged with using judgement and data both internal and external to the trial to make any irrevocable decision.

If the trial enrolls 30 participants, further enrollment will be paused until the DSMB reviews data on the primary outcome from all enrolled participants; a decision to continue enrollment will be made by the DSMB while the investigators remain blinded.

Stopping points:

We will conduct a futility analysis at 20 patients. If no efficacy is observed or the primary endpoint indicates worse outcomes, the study will be halted.

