### **3.7 Randomization and Blinding**

Participants confirmed to meet all eligibility criteria who have provided informed consent will be randomized 1:1 to magnesium citrate plus a the probiotic Floranex versus placebo. A randomization code will be provided to the site investigator or delegate from a centralized, web-based platform. Randomization will require provision of the screening number and confirmation of patient eligibility.

Randomization will be completed in permuted blocks of varying size and stratified by site. The randomized sequence allocation will be stored on a secure server and will not be available to site study personnel. Site research personnel will have a unique Personal Identification Number (PIN) to access the randomization system. Each subject will receive a computer-generated randomization ID number. The computer-generated randomization ID number will be provided to the pharmacy who will provide a dose pack containing magnesium citrate plus a the probiotic Floranex or placebo. The participant, treating clinicians, study personnel, and outcome assessors will all remain blinded to group assignment until after the database is locked and blinded analysis is completed.

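### The primary proportional odds model carries six slopes for 30 patients with no covariate priors: fitted by maximum likelihood or flat priors, it usually fails at 10 patients, is unstable at 20 and overstates a real effect at 30

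*Combined protocol and SAP*

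**What the plan says.** All of this is in section 7.1 of the combined protocol and SAP unless stated.

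- **Model.** "This analysis will be conducted with a proportional odds model using the Day 7 COVID Ordinal Outcome score as the dependent variable". Randomized group is the main term, and the covariates are "age, sex, baseline COVID Ordinal Outcome score, baseline SOFA score, and duration of acute respiratory infection symptoms prior to randomization".
- **Size.** "The anticipated study size is 30 patients", with reference to the "standard error of the log(odds-ratio) statistic with 15 patients per arm". That standard error, the target odds ratio and the power are not printed.
- **Looks.** "We calculated the sample size under the assumption that we would have an interim analysis after approximately each 10 patients". The stopping text lists one futility analysis before the end, at 20 patients, and leaves the number and timing of looks flexible.
- **Priors.** For efficacy, the treatment log odds ratio has a prior centred at 0 with standard error 0.352. The plan uses "a non-informative prior for tests of futility and harm".
- **Outcome scale.** Appendix E has 11 levels, 0 to 10. Table 1, used for planning, has four.

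The plan does not say which model the interim odds ratio comes from. It gives no prior or penalty for the covariates, and no rule for non-convergence or for dropping covariates.

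**The concern.** Treatment plus five covariates makes six slopes. Table 1's four categories add three cutpoints, so at least nine parameters would be estimated from 10, 20 or 30 patients. In samples this small, some combination of covariates often separates the outcome levels completely. The likelihood then has no finite maximum, and a flat prior does not repair that. Where a fit exists, an overfitted ordinal model pushes non-zero effects away from an odds ratio of 1 and understates their uncertainty.

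This is the primary analysis, and no fallback is named. If the same model feeds the monitoring, the futility and harm probabilities come from the prior choice that gives the fit no support. The text on the 20-patient look says the trial stops if efficacy is not seen or outcomes are worse, so an unstable estimate there could end it. Section 7.2 allows the plan to be modified, but picking another model after a failed fit would be a data-driven choice in the primary analysis.

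**Working it through.** **1. The plan's own figure.** The standard error behind 15 per arm is not printed, so 30 cannot be reproduced. It can be rebuilt for an unadjusted comparison from Table 1 (11.5, 5.8, 21.9 and 60.8%):

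- 1 − Σp³ = 1 − (0.0015 + 0.0002 + 0.0105 + 0.2248) = 0.763
- Information V = n₁n₂N / [3(N+1)²] × 0.763, and SE = 1/√V
- N = 30: V = 15×15×30/(3×961) × 0.763 = 1.786, so SE = 0.75
- N = 20: V = 1.153, SE = 0.93. N = 10: V = 0.526, SE = 1.38

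Using V ≈ N × 0.763/12, a standard error of 0.352 would need about 127 patients, so 0.352 is a prior width and not the 15-per-arm figure.

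**2. Information per slope.** Effective size is N × 0.763, or 7.6, 15.3 and 22.9 patients at N = 10, 20 and 30. Divided by six slopes, that is 1.3, 2.5 and 3.8 patients per slope.

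**3. Simulation of the stated model.** The fit was by maximum likelihood, with 1:1 allocation. The documents give no covariate distributions or effects, so these are assumptions. One set used age normal, sex 50/50, baseline score 4/5/6 at 30/50/20%, SOFA Poisson with mean 2, symptom duration uniform over 1-14 days, and covariate effects either absent or moderate. Another used log odds ratios per SD of 0.9 (baseline score), 0.4 (age), 0.4 (SOFA) and 0.2 (duration), with 0.2 for sex. Outcomes followed Table 1 or a finer split into 7 or 8 levels. Ranges over all runs:

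| | N = 10 | N = 20 | N = 30 |
|---|---|---|---|
| No finite or usable estimate | 63-92% | 0-20% | rare: fits in 97-100% at true OR 1 or 2 |
| SD of log OR where it fits (true OR 1) | not useful | 1.5-3.4 | 0.94-1.38 |
| Model SE too small by (true OR 1) | – | – | 15-27% |
| 95% interval misses (true OR 1) | – | – | roughly 6-9% in most scenarios |
| Median estimate, true OR 2 | – | – | 2.25-2.65 |

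At true OR 1 the estimate is centred correctly; it is only too variable. At true OR 3 the median at N = 30 is 4.0-4.4.

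**4. One scenario in detail** (N = 30, seven levels, moderate covariate effects):

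| Model | SD of log OR, OR 1 | Model SE (root mean square) | SE/SD | 95% miss | Harm rule met, flat treatment prior, OR 1 | Median, true OR 2 |
|---|---|---|---|---|---|---|
| Five covariates | 1.060 | 0.864 | 0.82 | 7.7% | 19.6% | e^0.911 = 2.49 |
| Baseline score only | 0.760 | 0.719 | 0.95 | 4.7% | 15.2% | e^0.694 = 2.00 |
| Unadjusted | 0.703 | 0.689 | 0.98 | 4.5% | 14.9% | e^0.655 = 1.93 |
| Five covariates, Normal(0,1) covariate priors, near-flat treatment prior (SD 10) | 0.865 | 0.788 | 0.91 | 5.8% | 17.2% | e^0.828 = 2.29 |

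In the same scenario at N = 20 with no effect, the five-covariate model has SD 2.55 against a model SE of 1.59, and meets the harm rule in 25.8% of trials (unadjusted 18.8%).

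**5. Effect of the 0.352 prior.** The weight on the data is 0.352²/(0.352² + SE²). At SE 0.75 this is 0.124/(0.124 + 0.560) = 0.18, and at SE 0.97 it is 0.12. An inflated estimate of 2.65 (log 0.975) then becomes a posterior odds ratio of about 1.1 to 1.2. At SE 0.75 an observed odds ratio of about 18 is needed to pass the 95% efficacy threshold, against 3.4 with a flat prior.

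**The case against.** **Looks and interim model.** A reader might infer that the DSMB is certain to receive an uninterpretable result at 10 patients. The documents do not go that far. The 10-patient look appears only as a sample-size assumption. Use of the covariate-adjusted model at interim looks is an inference, drawn because no other model is given.

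**Bayesian fit.** The monitoring is Bayesian, and proper priors on every coefficient would give a posterior at any size. That is correct, but the plan states no covariate priors and makes the treatment prior non-informative for two of its three rules. The failure rates therefore apply to maximum likelihood or flat priors.

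**Efficacy rule.** A reader might infer that inflation makes early stopping for efficacy too easy. It does not: the 0.352 prior shrinks the estimate to well below the assumed truth of 2.

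**Bias under no effect.** There is none. The inflation needs a true effect.

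**Eleven-level scale.** It is tempting to blame the number of levels, but finer outcomes help. At N = 10, non-fit was 66-71% with seven levels and 84-87% with four. The burden is the six slopes.

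**False harm signals.** Most come from the 70% threshold and the small sample. At N = 30 under no effect, the rule is met in 15-16% unadjusted and 19-22% with five covariates. The plan also calls its Bayesian stopping guidelines non-binding.

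These points narrow the concern. They do not remove the instability at 20 patients or the distortion at 30, and the plan names no fallback.

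**Conclusion.** The point holds in limited form and should be fixed before the first look. The primary model is too large for 30 patients unless its coefficients are regularised, and the plan regularises only the treatment effect, and only for efficacy. What is affected is the futility and harm probabilities, if they come from this model, and any odds ratio reported without the 0.352 prior. At 30 patients the damage is moderate: an interval that misses a few percentage points too often, and a true odds ratio of 2 reported at a median near 2.25-2.65. At 20 patients it is worse, and at 10 there is usually no estimate. The exact percentages rest on assumed covariate distributions, covariate effects and outcome splits, but the direction was the same in every main scenario.

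**What to change.** In section 7.1, name one model for the primary and interim analyses. Either:

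- use treatment plus baseline COVID Ordinal Outcome score, with the five-covariate model as a sensitivity analysis. In the runs with none or moderate covariate effects, this gave a median of 2.0-2.1 for a true odds ratio of 2 and interval misses of 4.7-5.3% under no effect at N = 30; or
- keep all five covariates with weakly informative priors on their standardised coefficients, for example Normal(0,1). With a near-flat treatment prior this fitted in at least 99.4% of trials at N = 10, but left slight inflation (median about 2.3) and misses of 5.1-6.9% at N = 30.

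In both cases, keep the stated 0.352 prior for efficacy; a weak prior there would loosen that rule. For futility and harm, replace the non-informative treatment prior with a wide proper one and state its SD. This is needed even with the smaller model, because baseline-only by maximum likelihood still fails in about 10-40% at N = 10. The SD matters: against the unadjusted SE of 1.38 at N = 10, an SD of 10 leaves the data a weight of 100/(100 + 1.90) = 0.98, while 1.5 leaves 2.25/(2.25 + 1.90) = 0.54.

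The cost is SAP wording and a short code change. A little prognostic information is dropped or shrunk.
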